#### **7.1.2.8 Patient Reported Outcomes (PROs)**

The EuroQol EQ-5D and EORTC QLQ-C30 questionnaires will be administered by trained site personnel and completed electronically by subjects in the following order: EuroQol EQ-5D first then EORTC QLQ-C30 at the time points specified in the Trial Flow Chart. It is most relevant and strongly recommended that ePROs are administered prior to drug administration, adverse event evaluation and disease status notification; an exception to this recommendation may occur at the treatment discontinuation visit where patients may have already been notified of their disease status or an AE evaluation is known prior to them arriving to the clinic.

The health economic assessment (HEA) form will be completed via an interview with the subject by qualified site personnel after the subject completes all other questionnaires. The form captures all non-study related health care contacts made throughout the study

#### **7.1.3 Laboratory Procedures/Assessments**

Details regarding specific laboratory procedures/assessments to be performed in this trial are provided below. The total amount of blood/tissue to be drawn/collected over the course of the trial (from pre-trial to post-trial visits), including approximate blood/tissue volumes drawn/collected by visit and by sample type per subject can be found in the Procedures Manual.

##### **7.1.3.1 Laboratory Safety Evaluations (Hematology, Chemistry and Urinalysis)**

Laboratory tests for hematology, chemistry and urinalysis are specified in [Table 6](#).

Table 6 Laboratory Tests

Hematology	Chemistry	Urinalysis	Other
Hematocrit	Albumin	Blood	Serum $\beta$ -human chorionic gonadotropin ( $\beta$ -hCG) a
Hemoglobin	Alkaline phosphatase	Glucose	PT (INR)
Platelet count	Alanine aminotransferase (ALT)	Protein	aPTT
WBC (total and differential) d	Aspartate aminotransferase (AST)	Specific gravity	Total triiodothyronine (T3) (or Free T3) b
Red Blood Cell Count	Carbon dioxide (CO 2 or bicarbonate) b	Microscopic exam, if abnormal results are noted	Free tyroxine (Free T4)
Absolute Neutrophil Count	Calcium	Urine pregnancy test a	Thyroid Stimulating Hormone (TSH)
Absolute Lymphocyte Count	Chloride		PK for pembrolizumab (MK-3475)
	Creatinine c (GFR can also be used in place of creatinine or CrCl)		Anti-pembrolizumab (MK-3475) Antibodies
	Glucose		Blood for correlative studies
	Phosphorus		Blood for FBR
	Potassium		Blood for Genetics
	Sodium		
	Total Bilirubin		
	Direct Bilirubin, if total bilirubin is elevated above the upper limit of normal		
	Total protein		
	Blood Urea Nitrogen e		
	Uric acid		

a Perform on women of childbearing potential only. If urine pregnancy results cannot be confirmed as negative, a serum pregnancy test will be required.

b If considered standard of care in your region

c For subjects with a baseline calculated creatinine clearance below the normal institutional laboratory range, a baseline measured creatinine clearance should be performed.

d For WBC results Absolute or % acceptable per their institutional standard.

e Blood Urea Nitrogen is preferred; if not available urea may be tested

Laboratory tests for screening should be performed within 10 days prior to the first dose of trial treatment. After Cycle 1, pre-dose laboratory procedures can be conducted up to 72 hours prior to dosing. Results must be reviewed by the investigator or qualified designee and found to be acceptable prior to each dose of trial treatment. The results from thyroid function tests (T3/or FT3, FT4, and TSH) are not required to be available nor reviewed prior to each dose of trial treatment after Cycle 1, unless clinical suspicion of thyroid dysfunction is observed.

### **7.1.3.2 Pharmacokinetic/Pharmacodynamic Evaluations**

The accumulation of robust PK and ADA data has allowed for the adequate characterization of the clinical pharmacology of pembrolizumab across indications. Therefore, upon approval of Amendment 3, each site is to stop the collection of PK and ADA samples for all subjects. Blood samples for PK and ADA collected prior to Amendment 3 may be stored only at this time. Analysis will be performed if required.

### **7.1.3.3 Future Biomedical Research**

The following specimens are to be obtained as part of Future Biomedical Research:

- Leftover DNA for future use
- Leftover tumor tissue
- Leftover biomarker samples

## **7.1.4 Other Procedures**

### **7.1.4.1 Withdrawal/Discontinuation**

When a subject discontinues/withdraws from participation in the trial, all applicable activities scheduled for the final trial visit should be performed at the time of discontinuation. Any adverse events which are present at the time of discontinuation/withdrawal should be followed in accordance with the safety requirements outlined in Section 7.2 - Assessing and Recording Adverse Events. Subjects who a) attain a CR or b) complete 24 months of treatment with pembrolizumab (MK-3475) may discontinue treatment with the option of restarting treatment if they meet the criteria specified in Section 7.1.5.2.1. After discontinuing treatment following assessment of CR or 24 months of treatment, these subjects should return to the site for a Safety Follow-up Visit (described in Section 7.1.5.3.1) and then proceed to the Follow-up Period of the study (described in Section 7.1.5.3.2).

#### **7.1.4.1.1 Withdrawal From Future Biomedical Research**

Subjects may withdraw their consent for Future Biomedical Research and have their specimens and all derivatives destroyed. Subjects may withdraw consent at any time by contacting the principal investigator for the main trial. If medical records for the main trial are still available, the investigator will contact the Sponsor using the designated mailbox ([contact]), and a form will be provided by the Sponsor to

obtain appropriate information to complete specimen withdrawal. Subsequently, the subject's specimens will be removed from the biorepository and be destroyed. A letter will be sent from the Sponsor to the investigator confirming the destruction. It is the responsibility of the investigator to inform the subject of completion of destruction. Any analyses in progress at the time of request for destruction or already performed prior to the request being received by the Sponsor will continue to be used as part of the overall research trial data and results. No new analyses would be generated after the request is received.

In the event that the medical records for the main trial are no longer available (e.g., if the investigator is no longer required by regulatory authorities to retain the main trial records) or the specimens have been completely anonymized, there will no longer be a link between the subject's personal information and their specimens. In this situation, the request for specimen destruction cannot be processed.

#### **7.1.4.2 Blinding/Unblinding**

This is an open label trial; there is no blinding for this trial.

#### **7.1.4.3 Calibration of Critical Equipment**

The investigator or qualified designee has the responsibility to ensure that any critical device or instrument used for a clinical evaluation/test during a clinical trial that provides important information about inclusion/exclusion criteria and/or safety or efficacy parameters shall be suitably calibrated and maintained to ensure that the data obtained is reliable and/or reproducible. Documentation of equipment calibration must be retained as source documentation at the trial site.

Critical Equipment for this trial includes:

- Laboratory equipment – as required for inclusion labs and trial assessments

See protocol-specified guidance in the Administrative Binder, Procedures Manual, Pharmacy Manual and Site Imaging Manual.

#### **7.1.5 Visit Requirements**

Visit requirements are outlined in Section 6.0 - Trial Flow Chart. Specific procedure-related details are provided above in Section 7.1 - Trial Procedures.

##### **7.1.5.1 Screening**

Approximately 28 days prior to randomization number assignment, potential subjects will be evaluated to determine that they fulfill the entry requirements as set forth in Section 5.1. Screening procedures may be repeated after consultation with the Sponsor.

Results of a test performed prior to the subject signing consent as part of routine clinical management are acceptable in lieu of a screening test if performed within the specified time

frame. Screening procedures are to be completed within 28 days prior to the first dose trial treatment except for the following:

- Informed Consent Form (ICF) signed prior to completing any protocol specified procedure.
- Laboratory tests and evaluation of ECOG status are to be performed within 10 days prior to the first dose of trial treatment
- For women of reproductive potential, a urine pregnancy test will be performed within 72 hours prior to the first dose of trial treatment. If urine pregnancy results cannot be confirmed as negative, a serum pregnancy test will be required (performed by the local study site laboratory).
- Initial tumor imaging must be performed within 28 days of the first dose of study.
- A “newly obtained” tissue sample may be obtained at any time before the first dose of study drug, as long as the subject has not received any intervening systemic therapy from the time the tissue was collected until the time the subject enters the study. See Section 7.1.2.7 for additional details regarding tumor tissue requirements.

Subjects may be rescreened after initially failing to meet the inclusion/exclusion criteria. Results from assessments performed during the initial screening period are acceptable in lieu of a repeat screening test if performed within the specified time frame and the inclusion/exclusion criteria is met.

#### **7.1.5.2 Treatment Period/Vaccination Visit**

Visit requirements are outlined in Section 6.0 – Trial Flow Chart. Specific procedure-related details are provided above in Section 7.1 – Trial Procedures.

##### **7.1.5.2.1 Second Course Phase (Retreatment Period)**

Subjects who stop pembrolizumab (MK-3475) with SD or better may be eligible for up to one year of additional pembrolizumab (MK-3475) therapy if they progress after stopping study treatment. This retreatment is termed the Second Course Phase of this study and is only available if the study remains open and the subject meets the following conditions:

- **Either**
  - Stopped initial treatment with pembrolizumab (MK-3475) after attaining an investigator-determined confirmed CR according to RECIST 1.1
    - Was treated for at least 24 weeks with pembrolizumab (MK-3475) before discontinuing therapy
    - Received at least two treatments with pembrolizumab (MK-3475) beyond the date when the initial CR was declared

**OR**

- Subject had SD, PR or CR and stopped pembrolizumab (MK-3475) treatment after 24 months of trial treatment for reasons other than disease progression or intolerability

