### SUMMARY OF CHANGES

#### PRIMARY REASON FOR THIS AMENDMENT:

Section Number	Section Title	Description of Change	Rationale
5.2.1.2	Immune-Related Events and Dose Modification (Withhold, Treat, Discontinue)	The dose modification and toxicity management guidelines for irAEs and table were updated.	The dose modification and toxicity management guidelines for irAEs and table were updated as requested by the U.S. Food and Drug Administration (FDA) in an effort to harmonize the presentation of safety information across all FDA-approved programmed cell death 1/ ligand 1 (PD-1/L1) antibody prescribing information.

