### **5.2.1.2 Immune-Related Events and Dose Modification (Withhold, Treat, Discontinue)**

#### **Dose Modification and Toxicity Management for Immune-related AEs Associated with Pembrolizumab**

AEs associated with pembrolizumab exposure may represent an immune-related response. These irAEs may occur shortly after the first dose or several months after the last dose of pembrolizumab treatment and may affect more than one body system simultaneously. Therefore, early recognition and initiation of treatment is critical to reduce complications. Based on existing clinical study data, most irAEs were reversible and could be managed with interruptions of pembrolizumab, administration of corticosteroids and/or other supportive care. For suspected irAEs, ensure adequate evaluation to confirm etiology or exclude other causes. Additional procedures or tests such as bronchoscopy, endoscopy, skin biopsy may be included as part of the evaluation. Based on the severity of irAEs, withhold or permanently discontinue pembrolizumab and administer corticosteroids.

Dose Modification and Toxicity Management Guidelines for irAEs associated with pembrolizumab monotherapy, coformulations, or IO combinations are provided in [Table 3](#).

**Table 3 Dose Modification and Toxicity Management Guidelines for Immune-related Adverse Events Associated with Pembrolizumab Monotherapy, Coformulations or IO Combinations**

General instructions:
 
 
1. Severe and life-threatening irAEs should be treated with IV corticosteroids followed by oral steroids. Other immunosuppressive treatment should begin if the irAEs are not controlled by corticosteroids.
 
2. Pembrolizumab monotherapy, coformulations or IO combinations must be permanently discontinued if the irAE does not resolve or the corticosteroid dose is not <math>\leq 10</math> mg/day within 12 weeks of the last treatment.
 
3. The corticosteroid taper should begin when the irAE is <math>\leq</math> Grade 1 and continue at least 4 weeks.
 
4. If pembrolizumab monotherapy, coformulations or IO combinations have been withheld, treatment may resume after the irAE decreased to <math>\leq</math> Grade 1 after corticosteroid taper.
 
				
irAEs	Toxicity Grade (CTCAEv4.0)	Action With Pembrolizumab Monotherapy, Coformulations or IO Combinations	Corticosteroid and/or Other Therapies	Monitoring and Follow-up

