### **5.5.2 Prohibited Concomitant Medications**

Subjects are prohibited from receiving the following therapies during the Screening and Treatment Phase (including retreatment for post-complete response relapse) of this trial:

- Antineoplastic systemic chemotherapy or biological therapy
- Immunotherapy not specified in this protocol
- Chemotherapy not specified in this protocol
- Investigational agents other than pembrolizumab (MK-3475)
- Radiation therapy
  - Note: Radiation therapy to a symptomatic solitary lesion or to the brain may be allowed after consultation with Sponsor.
- Live vaccines within 30 days prior to the first dose of trial treatment and while participating in the trial. Examples of live vaccines include, but are not limited to, the following: measles, mumps, rubella, varicella/zoster, yellow fever, intranasal influenza, rabies, BCG, and typhoid vaccine.
- Systemic glucocorticoids for any purpose other than to modulate symptoms from an event of clinical interest of suspected immunologic etiology. Subjects who require corticosteroids to manage drug-related adverse events must be at an equivalent dose of  $\leq 10$  mg per day of prednisone to resume dosing with MK-3475. Furthermore, an inability to reduce the corticosteroid dose for managing a drug-related adverse event to the equivalent of  $\leq 10$  mg prednisone per day within 12 weeks of last MK-3475 dose should prompt discussion between the investigator and Sponsor regarding the subject's ability to continue on treatment in the trial.
  - Note: Temporary use of prophylactic corticosteroids to avoid allergic reactions (e.g. IV contrast dye or transfusions) is permitted.
  - Note: Use of intermittent inhaled steroids or local injection of corticosteroids is permitted upon consultation with the sponsor.

Subjects who, in the assessment by the investigator, require the use of any of the aforementioned treatments for clinical management should be removed from the trial.

Subjects may receive other medications that the investigator deems to be medically necessary.

The Exclusion Criteria describes other medications, which are prohibited in this trial.

There are no prohibited therapies during the Post-Treatment Follow-up Phase.

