### **7.1.1.8 Trial Compliance (Medication/Diet/Activity/Other)**

Interruptions from the protocol specified treatment plan for greater than 12 weeks between pembrolizumab (MK-3475) doses require consultation between the investigator and the Sponsor and written documentation of the collaborative decision on subject management.

Administration of trial medication will be witnessed by the investigator and/or trial staff. The total volume of pembrolizumab (MK-3475) infused will be compared to the total volume prepared to determine compliance to each dose of pembrolizumab (MK-3475) administered. The instructions for preparing and administering pembrolizumab (MK-3475) will be provided in the Pharmacy Manual.

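### When steroids for an immune-related AE are not down to 10 mg/day within 12 weeks, Table 3 requires permanent discontinuation but Section 5.5.2 only calls for a discussion

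*Combined protocol and SAP*

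**What the plan says.** Table 3, general instruction 2 (Section 5.2.1.2), states that pembrolizumab "must be permanently discontinued if the irAE does not resolve or the corticosteroid dose is not" at or below 10 mg/day by 12 weeks after the last treatment.

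Section 5.5.2 lists therapies that are prohibited "during the Screening and Treatment Phase (including retreatment for post-complete response relapse) of this trial". The list includes "Systemic glucocorticoids for any purpose other than to modulate symptoms from an event of clinical interest of suspected immunologic etiology", with exceptions for allergy prophylaxis and for inhaled or locally injected steroids. It then sets two rules for subjects who need steroids for a drug-related adverse event. Dosing may resume only at 10 mg/day or less of prednisone equivalent. Failure to reach that dose within 12 weeks of the last MK-3475 dose "should prompt discussion between the investigator and Sponsor regarding" whether the subject can stay on treatment.

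Section 7.1.1.8 adds: "Interruptions from the protocol specified treatment plan for greater than 12 weeks between pembrolizumab (MK-3475) doses require consultation between the investigator and the Sponsor", with written documentation of the decision.

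Section 7.1.5.2.1 governs entry to the Second Course. One route requires that the subject "Stopped initial treatment with pembrolizumab (MK-3475) after attaining an investigator-determined confirmed CR according to RECIST 1.1", with at least 24 weeks of treatment and at least two doses after the complete response (CR). The other requires that the subject "stopped pembrolizumab (MK-3475) treatment after 24 months of trial treatment for reasons other than disease progression or intolerability".

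**The concern.** Permanent discontinuation after a steroid course that cannot be tapered is a subject-protection rule. If one section makes it mandatory and another treats the same situation as open to discussion, a site that reads only the concomitant-medication section may keep dosing a subject whom Table 3 takes off the drug for good. Investigators look up steroid rules in 5.5.2 as naturally as in Table 3, so the softer wording is not out of the way. At stake are the safety of individual subjects and consistent conduct across sites; no sample size or analysis figure depends on it.

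**Working it through.** No arithmetic applies to the conflict itself. The two rules side by side:

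| Element | Table 3, general instruction 2 | Section 5.5.2 |
|---|---|---|
| Event | irAE | Drug-related adverse event treated with steroids |
| Dose threshold | 10 mg/day | 10 mg/day prednisone equivalent |
| Clock | 12 weeks from last treatment | 12 weeks from last MK-3475 dose |
| Action if missed | Permanent discontinuation, mandatory | Investigator and Sponsor discuss continuing |

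1. **Threshold and clock.** They are the same, reading Table 3's figure as prednisone equivalent. The instruction does not name the steroid, but the Table 3 rows that give a starting dose give it as prednisone or equivalent.

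2. **Events.** Apart from its stated exceptions, 5.5.2 permits systemic glucocorticoids only for events of suspected immune cause, which is largely the territory of Table 3. The overlap is not complete. An event first suspected to be immune-related, then judged drug-related but not immune-related, falls under 5.5.2 alone, because the note under Table 3 leaves non-irAEs to clinical practice.

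3. **Where the answers part.** Take a subject with an irAE who is above 10 mg/day at week 12 and gets down to 10 mg/day some weeks later. Under Table 3 the drug is already permanently stopped. Under 5.5.2 the resumption dose is now met and the only consequence of missing week 12 was a discussion. A site that discusses and stops satisfies both rules. A site that discusses and resumes satisfies 5.5.2 and breaches Table 3.

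4. **Does another section rank them?** Section 5.8 makes unacceptable adverse experiences under 5.2.1.2 a mandatory reason to stop treatment, and 5.6.1 sends the reader to 5.2.1.2 for dose modification. Both favour Table 3. However, 5.8 also lets a discontinued subject restart when that is judged medically appropriate, and neither section mentions 5.5.2. Section 7.1.1.8 requires consultation and a record for long gaps; it neither permits redosing after a mandatory stop nor forbids it. The Summary of Changes shows that the current amendment revised only 5.2.1.2, at the FDA's request, so 5.5.2 was not revisited with it. Both texts are in force.

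5. **How far the conflict extends.** Mandatory permanent-discontinuation rules: general instruction 2 (1), Table 3 rows for pneumonitis, diarrhea/colitis, AST/ALT/bilirubin, nephritis, myocarditis and all other irAEs (6), and Table 4 rules for Grade 2 despite premedication and for Grade 3 or 4 (2). The total is 1 + 6 + 2 = 9. Section 5.5.2 contradicts 1 of the 9. The hypophysitis and hyperthyroidism rows are not counted because footnote a lets treatment resume.

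**The case against.** The best defence is that the two rules can be obeyed together: hold the discussion, then stop the drug. Section 5.5.2 is a list of concomitant medications and does not authorise continued dosing, while 5.8 and 5.6.1 point to 5.2.1.2. A careful site would follow the mandatory rule. This stands to the extent that one course of action satisfies both sections, and it makes the problem smaller than an outright clash. It does not remove it. A discussion about whether a subject can continue presupposes that continuing is possible, which Table 3 rules out, and no sentence tells the reader that Table 3 prevails.

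It can also be said that the triggers differ, since 5.5.2 speaks of drug-related events and Table 3 of irAEs. That stands, and it means the correction must be confined to irAEs. Making discontinuation mandatory for every drug-related event would create a rule that Table 3 does not contain.

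A reader might go further and infer that 5.5.2, by mentioning retreatment after CR, lets a CR subject whom Table 3 has permanently discontinued back in through the Second Course. The documents do not support that. The retreatment phrase says when the listed therapies are prohibited; it does not say who may restart. Section 5.8.2 describes stopping after CR as an elective choice. The CR route in 7.1.5.2.1 does omit the intolerability exclusion found in the 24-month route and does not cite 5.2.1.2, but nothing in 5.5.2 sets aside a permanent discontinuation at that point. The retreatment conditions also include an investigator best-interest judgement, and Table 7 requires Sponsor approval before rechallenge after a serious event that the drug may have caused.

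**Conclusion.** The inconsistency is real and worth correcting. For an irAE with steroids not tapered to 10 mg/day within 12 weeks of the last dose, Section 5.5.2 leaves open a decision that Table 3, general instruction 2, closes. It bears mainly on dosing during treatment, whether in the first course or in retreatment already under way. It is not a flaw in Second Course eligibility, where at most a cross-reference is missing.

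The conclusion assumes that Table 3's dose means prednisone equivalent and that the event is judged immune-related. The number of subjects affected cannot be derived, because the documents give no rate of steroid courses lasting beyond 12 weeks. Section 5.8.2 states that Second Course response or progression does not count towards the primary ORR, so nothing decided in that phase changes the primary endpoint.

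**What to change.** In Section 5.5.2, replace the consequence at 12 weeks with two cases:

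- For irAEs, failure to reduce to 10 mg/day or less of prednisone equivalent within 12 weeks of the last dose requires permanent discontinuation under Table 3, general instruction 2 (Section 5.2.1.2).
- For drug-related events judged not to be immune-related, the investigator and Sponsor discuss whether treatment can continue, as now.

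Tables 3 and 4 stay as they are. Table 3 should govern because it carries the mandatory rule and is the text most recently revised.

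An optional clarification, not needed for this point, is a bullet in 7.1.5.2.1 stating that subjects permanently discontinued under Table 3 or Table 4 may not enter the Second Course, except where footnote a of Table 3 permits resumption. A general intolerability bar on the CR route is not proposed; that is a clinical choice for the Sponsor.

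The cost is a short wording change. Some subjects with irAEs, probably few, lose the discussion route that 5.5.2 now gives them, although Table 3 already denies it.
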